## 8.2. Adverse Events and Serious Adverse Events

Local injection site solicited AEs will include pain, redness and swelling, and will be assessed after dosing at Visit 1 for 7 days (IM recipients only). If more than 1 injection is given, reactions will be assessed separately at each injection site.

Systemic solicited AEs will be assessed in all participants after dosing at Visit 1 and recorded for 7 days. These will include fever, headache, fatigue, muscle aches, nausea, vomiting, diarrhea, and joint pain.

Site staff will document any AEs in the study source during the confinement for all cohorts. The site staff will record solicited injection site AEs (IM doses only) and solicited systemic AEs (all participants), including duration and intensity, during confinement. Refer to Section 8.1.9 for solicited AEs to be recorded in the diary card by participants, through Day 7.

Solicited AEs that continue beyond Day 7 will be captured in the unsolicited AEs memory aid and marked as continuation of solicited AE. Participants will be asked to record events at the same time each evening.

Unsolicited AEs including AESIs, SAEs, and safety laboratory parameters Grade 1 and above will be collected from screening through Day 151 and recorded in the AE log by the study team.

The definitions of AEs, SAEs, serious adverse drug reactions (ADRs) and AESIs can be found in Appendix 2, Section 10.2.1, and 10.2.2, 10.2.3, 10.2.4, respectively.

Refer to Appendix 2, Section 10.2 for details regarding AEs, AESIs, and SAEs and Section 10.4 (Table 9) for laboratory parameters.

Immediate safety concerns should be discussed with the sponsor, and the SRT. The SRT will trigger an IDMC review if any pausing rule is met (see Section 8.2.7 for IDMC and Section 10.2.5 for details regarding AE reporting and follow-up).

AEs will be reported by the participant (or, as appropriate, the participant's legally authorized representative). Clinical chemistry and/or hematology results may also qualify as AEs (Section 10.4, Appendix 4).

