#### Events Meeting the AE Definition

Any abnormal laboratory test results (hematology, clinical chemistry, or urinalysis) or other safety assessments (e.g., ECG, radiological scans, vital signs measurements), including those that worsen from baseline, considered clinically significant in the medical and scientific judgment of the investigator (i.e., not related to progression of underlying disease).

Exacerbation of a chronic or intermittent pre-existing condition including either an increase in frequency and/or intensity of the condition.

New conditions detected or diagnosed after study intervention administration even though it may have been present before the start of the study.

Signs, symptoms, or the clinical sequelae of a suspected drug-drug interaction.

Signs, symptoms, or the clinical sequelae of a suspected overdose of either study intervention or a concomitant medication. Overdose per se will not be reported as an AE/SAE unless it is an intentional overdose taken with possible suicidal/self-harming intent. Such overdoses should be reported regardless of sequelae.

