**Table 9: FDA Toxicity Grading Scale- Laboratory Abnormalities**

Serum *	Mild (Grade 1)	Moderate (Grade 2)	Severe (Grade 3)	Potentially Life Threatening (Grade 4)**
Sodium – Hyponatremia mEq/L	132 – 134	130 – 131	125 – 129	< 125
Sodium – Hypernatremia mEq/L	144 – 145	146 – 147	148 – 150	> 150
Potassium – Hyperkalemia mEq/L	5.1 – 5.2	5.3 – 5.4	5.5 – 5.6	> 5.6
Potassium – Hypokalemia mEq/L	3.5 – 3.6	3.3 – 3.4	3.1 – 3.2	< 3.1
Glucose – Hypoglycemia mg/dL	65 – 69	55 – 64	45 – 54	< 45
Glucose – Hyperglycemia	100 – 110	111 – 125	>125	Insulin requirements or hyperos-molar coma
Fasting – mg/dL	110 – 125	126 – 200	>200	
Random – mg/dL				
Blood Urea Nitrogen BUN mg/dL	23 – 26	27 – 31	> 31	Requires dialysis
Creatinine – mg/dL	1.5 – 1.7	1.8 – 2.0	2.1 – 2.5	> 2.5 or requires dialysis
Calcium – hypocalcemia mg/dL	8.0 – 8.4	7.5 – 7.9	7.0 – 7.4	< 7.0
Calcium – hypercalcemia mg/dL	10.5 – 11.0	11.1 – 11.5	11.6 – 12.0	> 12.0
Magnesium – hypomagnesemia mg/dL	1.3 – 1.5	1.1 – 1.2	0.9 – 1.0	< 0.9
Phosphorous – hypophosphatemia mg/dL	2.3 – 2.5	2.0 – 2.2	1.6 – 1.9	< 1.6
CPK – mg/dL	1.25 – 1.5 x ULN***	1.6 – 3.0 x ULN	3.1 – 10 x ULN	> 10 x ULN
Albumin – Hypoalbuminemia g/dL	2.8 – 3.1	2.5 – 2.7	< 2.5	--
Total Protein – Hypoproteinemia g/dL	5.5 – 6.0	5.0 – 5.4	< 5.0	--
Alkaline phosphate – increase by factor	1.1 – 2.0 x ULN	2.1 – 3.0 x ULN	□ 3.1 – 10 x ULN	> 10 x ULN
Liver Function Tests –ALT, AST increase by factor	1.1 – 2.5 x ULN	2.6 – 5.0 x ULN	5.1 – 10 x ULN	> 10 x ULN
Bilirubin – when accompanied by any increase in Liver Function Test increase by factor	1.1 – 1.25 x ULN	1.26 – 1.5 x ULN	1.51 – 1.75 x ULN	> 1.75 x ULN
Bilirubin – when Liver Function Test is normal; increase by factor	1.1 – 1.5 x ULN	1.6 – 2.0 x ULN	2.0 – 3.0 x ULN	> 3.0 x ULN
Cholesterol	201 – 210	211 – 225	> 226	---
Pancreatic enzymes – amylase, lipase	1.1 – 1.5 x ULN	1.6 – 2.0 x ULN	2.1 – 5.0 x ULN	> 5.0 x ULN

\* The laboratory values provided in the tables serve as guidelines and are dependent upon institutional normal parameters. Institutional normal reference ranges should be provided to demonstrate that they are appropriate.

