\*\* The clinical signs or symptoms associated with laboratory abnormalities might result in characterization of the laboratory abnormalities as potentially life-threatening (Grade 4). For example, a low sodium value that falls within a Grade 3 parameter (125-129 mEq/L) should be recorded as a Grade 4 hyponatremia event if the participant had a new seizure associated with the low sodium value.

\*\*\*ULN is the upper limit of the normal range.

**Table 9: FDA Toxicity Grading Scale- Laboratory Abnormalities, continued...**

Hematology *	Mild (Grade 1)	Moderate (Grade 2)	Severe (Grade 3)	Potentially Life Threatening (Grade 4)
Hemoglobin (Female) - gm/dL	11.0 – 12.0	9.5 – 10.9	8.0 – 9.4	< 8.0
Hemoglobin (Female) change from baseline value - gm/dL	Any decrease – 1.5	1.6 – 2.0	2.1 – 5.0	> 5.0
Hemoglobin (Male) - gm/dL	12.5 – 13.5	10.5 – 12.4	8.5 – 10.4	< 8.5
Hemoglobin (Male) change from baseline value – gm/dL	Any decrease – 1.5	1.6 – 2.0	2.1 – 5.0	> 5.0
WBC Increase - cell/mm 	10,800 – 15,000	15,001 – 20,000	20,001 – 25,000	> 25,000
WBC Decrease - cell/mm 	2,500 – 3,500	1,500 – 2,499	1,000 – 1,499	< 1,000
Lymphocytes Decrease - cell/mm 	750 – 1,000	500 – 749	250 – 499	< 250
Neutrophils Decrease - cell/mm 	1,500 – 2,000	1,000 – 1,499	500 – 999	< 500
Eosinophils - cell/mm 	650 – 1500	1501 – 5000	> 5000	Hypereosinophilic
Platelets Decreased - cell/mm 	125,000 – 140,000	100,000 – 124,000	25,000 – 99,000	< 25,000
PT – increase by factor (prothrombin time)	1.0 – 1.10 x ULN**	□ 1.11 – 1.20 x ULN	1.21 – 1.25 x ULN	> 1.25 ULN
PTT – increase by factor (partial thromboplastin time)	1.0 – 1.2 x ULN	1.21 – 1.4 x ULN	1.41 – 1.5 x ULN	> 1.5 x ULN
Fibrinogen increase - mg/dL	400 – 500	501 – 600	> 600	--
Fibrinogen decrease - mg/dL	150 – 200	125 – 149	100 – 124	< 100 or associated with gross bleeding or disseminated intravascular coagulation (DIC)

WBC= white blood cell count

\* The laboratory values provided in the tables serve as guidelines and are dependent upon institutional normal parameters. Institutional normal reference ranges should be provided to demonstrate that they are appropriate.

\*\* “ULN” is the upper limit of the normal range.

GGT grading is not provided in the FDA toxicity grading scale tables. The following grading scale is from the U.S. Department of Health and Human Services, Common Terminology Criteria for Adverse Events, Version 5.0 [US HHS 2017]:

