9.2 Clinical Laboratory Evaluations

The following laboratory tests will be performed:

Hematology	Complete blood count (including hemoglobin, platelet count and white blood cell count) and absolute counts for neutrophils, lymphocytes, eosinophils, and monocytes.
Serum Chemistry	Alanine aminotransferase (ALT), aspartate aminotransferase (AST), alkaline phosphatase, total bilirubin, gamma glutamyl transferase (GGT), creatinine, blood urea nitrogen, lactate dehydrogenase (LDH), glucose, albumin, sodium, potassium, chloride, bicarbonate, and calcium.
Urinalysis	Specific gravity, pH, glucose, protein, blood, ketones, bilirubin, urobilinogen, nitrite, leukocyte esterase by dipstick.
Other tests	HIV, hepatitis B and C, urine drug screen, and serum pregnancy test (females only)

The hematology, serum chemistry, and urinalysis tests will be performed at the timepoints indicated in the schedule of assessments (schedule of assessments can be found in [Section 15](#)).

All laboratory values collected at visits will be included in the summaries and listings.

Descriptive summaries of observed value and change from baseline (last result available on or before Day 1) at each scheduled post baseline visit will be presented by treatment group for each continuous parameter for the safety population, both in tabular format and as boxplots. For participants who have an abnormal on-study laboratory result, longitudinal (spider) plots for hematology, serum chemistry, and urinalysis parameters will be produced.

Tables of the worst shift in FDA Toxicity Grading Scale in laboratory values from Day 1 (baseline) to visit Day 8, visit Day 91, visit Day 151 will be also presented per parameter, for those parameters that have FDA Toxicity Grading Scale grading. Values that aren't within any toxicity criteria will be presented as 'Normal'.

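### The laboratory shift tables label uncovered out-of-range values as 'Normal', leave out GGT, and do not say which haemoglobin criterion applies

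*SAP*

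**What the plan says.** The protocol defines its secondary laboratory endpoint by grade: parameters at Grade 1 and above up to Day 151 (Protocol Section 3, Table 4; repeated in Table 7). Protocol 9.3.2 also plans a frequency of values outside the normal range by treatment group. SAP 2.2 lists the same endpoint without the grade qualifier.

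SAP 9.2 plans continuous summaries, boxplots, spider plots for participants with an abnormal on-study result, and worst-shift tables from baseline to Days 8, 91 and 151. It adds that "All laboratory values collected at visits will be included in the summaries and listings". The shift tables are produced "for those parameters that have FDA Toxicity Grading Scale grading". Values not "within any toxicity criteria will be presented as" 'Normal'.

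The grades are in Protocol 10.4:
- The row "Liver Function Tests –ALT, AST increase by factor" runs 1.1-2.5 (Grade 1), 2.6-5.0 (Grade 2), 5.1-10 (Grade 3) and above 10 x ULN (Grade 4).
- Haemoglobin has two rows per sex, one on the absolute value and one on change from baseline. Grade 1 of the change row is "Any decrease – 1.5" g/dL.
- A note states that "GGT grading is not provided in the FDA toxicity grading scale tables", and gives CTCAE v5.0 grades for GGT instead.

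On AEs, Protocol 8.2 says "safety laboratory parameters Grade 1 and above will be collected from screening through Day 151 and recorded in the AE log". Protocol 10.2.1 counts an abnormal laboratory result as an AE when it is "considered clinically significant in the medical and scientific judgment of the investigator".

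**The concern.** The worst-shift table is the only categorical laboratory output in SAP 9.2, so it carries the grade-based endpoint. Three features of it are unsafe.

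- A value in a gap between two grades, or just above ULN, is given the label 'Normal'. If it is the participant's highest value, the worst shift is then taken from a lower one.
- A parameter for which the protocol supplies grades gets no graded table.
- The haemoglobin row is left to the programmer. One of the two choices would make Grade 1 or above the usual result in people with no true change.

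If Grade 1 laboratory values were also entered as AEs, as one reading of Protocol 8.2 allows, the third problem could reach the primary AE incidence.

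**Working it through.** **The plan's own figure.** The only sample-size figure is the chance of seeing at least one AE, 1-(1-p)^n. It reproduces: 1-(1-0.2353)^6 = 0.800 and 1-(1-0.3187)^6 = 0.900; for n=24, 0.800 at 6.49% and 0.900 at 9.15%; for n=48, 0.800 at 3.3% and 0.900 at 4.68%. The documents give no figure for laboratory grading.

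**Liver gaps.** Inputs are the Table 9 ALT/AST bands and an assumed ULN, since the documents give none. The ratio is value/ULN. No band covers >1.0 to <1.1, >2.5 to <2.6 or >5.0 to <5.1. At ULN 40 U/L:

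| ALT (U/L) | Ratio | Literal reading | Ratio rounded to 0.1 (half up) |
|---|---|---|---|
| 41 | 1.025 | Normal | Normal (1.0) |
| 42-43 | 1.050-1.075 | Normal | Grade 1 (1.1) |
| 100 | 2.500 | Grade 1 | Grade 1 |
| 101 | 2.525 | Normal | Grade 1 (2.5) |
| 102-103 | 2.550-2.575 | Normal | Grade 2 (2.6) |
| 104 | 2.600 | Grade 2 | Grade 2 |
| 200 | 5.000 | Grade 2 | Grade 2 |
| 201 | 5.025 | Normal | Grade 2 (5.0) |
| 202-203 | 5.050-5.075 | Normal | Grade 3 (5.1) |
| 204 | 5.100 | Grade 3 | Grade 3 |

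Over assumed ULNs of 30 to 55 U/L, 6 to 15 integer values between ULN and 10 x ULN are labelled Normal on the literal reading, and 1 or 2 after rounding.

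**Other analytes.**
- Alkaline phosphatase (bands 1.1-2.0, 2.1-3.0, 3.1-10) at an assumed ULN of 120 leaves 121-131, 241-251 and 361-371 uncovered.
- Bilirubin with normal liver tests (1.1-1.5, 1.6-2.0, 2.0-3.0) is both Grade 2 and Grade 3 at exactly 2.0 x ULN. At an assumed ULN of 1.2 mg/dL, 1.3 and 1.9 are uncovered.
- Bilirubin with raised liver tests has cut-points at 1.25, 1.5 and 1.75, with gaps only 0.01 wide between grades.
- Table 10 stops at 2+ for urine protein and glucose, so a 3+ without hospitalisation fits no cell.

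**GGT.** SAP 9.2 restricts the shift tables to FDA-graded parameters, and the note to Table 9 says GGT is not one of them. GGT is therefore absent from the shift tables but present in SAP 9.2's list of tests, and so in the continuous outputs.

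**Haemoglobin, if the change row is used.** There is one baseline and three scheduled post-baseline visits. With no true change and exchangeable continuous readings, the chance that baseline is the lowest of four is 1/4. The chance of at least one fall is then 1-1/4 = 75%: about 0.75 x 48 = 36 on RSM01, 0.75 x 8 = 6 on placebo, and 42 of 56 overall.

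Reporting to 0.1 g/dL creates ties, which lower this. Simulated results for assumed within-person SDs, which the documents do not give:

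| SD (g/dL) | Fall at one visit | Fall at any of three | Any of three, with a 0.2 g/dL downward drift |
|---|---|---|---|
| 0.2 | 42.9% | 67.9% | 89.9% |
| 0.3 | 45.3% | 70.6% | 85.9% |
| 0.4 | 46.5% | 71.7% | 83.6% |
| 0.5 | 47.2% | 72.3% | 82.2% |
| 0.6 | 47.7% | 72.8% | 81.0% |

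**AE route, conditional.** If every such fall became an AE, the chance of at least one AE in six participants would be 1-0.25^6 = 0.9998 with no drug effect. That applies only if Protocol 8.2 is followed over 10.2.1.

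**The case against.** The strongest reply is that these are matters of wording and that the data stay visible. Much of that stands.

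- *A reader might infer that liver signals are hidden.* The documents do not support this. The 'Normal' label applies to the shift tables only. An ALT of 203 U/L still enters the continuous summaries, boxplots and listings, and under Protocol 8.1.7 the investigator reviews each laboratory report.
- *A reader might infer that GGT is dropped from the analysis.* It is missing only from the graded tables.
- *The gaps between grades come from a literal reading.* Table 9 gives the ALT/AST bands to one decimal, and grading at that precision closes them. But the SAP does not state this rule, and the band just above ULN stays open even then. Table 9 calls its values guidelines, so the SAP needs a programmable rule.
- *A reader might infer that haemoglobin noise will dominate the endpoint.* That follows only if the change row is used. A baseline-to-visit shift fits the absolute row more naturally, because a change has no grade at baseline. The noise would fall on RSM01 and placebo alike, and larger falls are graded higher and remain distinguishable.
- *A reader might infer that the primary AE endpoint is distorted.* Protocol 8.2 also refers to Appendix 2 for details, and 8.1.7 and 10.2.1 both filter on clinical relevance or significance. The trial is descriptive and not powered for safety differences (Protocol 9.1), so a claim that real differences would be masked goes too far.

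What remains is that a stated SAP rule gives wrong labels, and a protocol-graded parameter has no graded output.

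**Conclusion.** The point holds for the graded part of the secondary laboratory endpoint and should be fixed. Followed as written, SAP 9.2 labels some out-of-range values Normal: nine integer ALT values at an assumed ULN of 40 U/L, or one if ratios are rounded to 0.1. The documents give no ALT distribution, so this cannot be turned into an expected number of participants. GGT has no graded table although the protocol provides its grades, and SAP 9.2 has no counterpart to the protocol's out-of-range frequency that would make up for either gap.

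The haemoglobin effect is conditional on an unstated choice of row. Its size, about 68-75% at Grade 1 or above by chance, assumes no drift, exchangeable readings and an SD of 0.2-0.6 g/dL. It inflates Grade 1 incidence in both arms and does not bias the comparison between them. Protocol 8.2 and 10.2.1 conflict on when a laboratory value is an AE. Any effect on the primary endpoint depends on how that is settled and should not be asserted now.

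**What to change.** In SAP 9.2:
1. Grade ULN ratios after rounding to the precision of the relevant Table 9 row, stating the rounding convention, or use contiguous boundaries at each analyte's own Table 9 cut-points. ALT cut-points must not be carried over to alkaline phosphatase or bilirubin. Resolve the bilirubin overlap at 2.0 x ULN.
2. Reserve 'Normal' for values within the reference range. Label other uncovered values 'Outside range, not graded'.
3. Add GGT shift tables using the CTCAE v5.0 grades in Protocol 10.4.
4. Base haemoglobin shifts on the absolute row and tabulate the change row separately.
5. Restore the outside-normal-range frequency table planned in Protocol 9.3.2.

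In the protocol, reconcile Section 8.2 with 10.2.1 so that the rule for recording a graded laboratory value as an AE is unambiguous.

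The cost is a few lines of SAP text, changes to the grading code, and one protocol clarification. No new data are needed.

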9.3 Vital Sign Measurements

Vital signs will include systolic and diastolic blood pressure, pulse rate, and body temperature, and percent oxygen saturation and will be measured at the timepoints indicated in the schedule of assessments (see [Section 15](#)). Vital signs are to be taken after at least 5 minutes of rest in a quiet setting without distractions. Measurements are to be repeated if clinically significant changes are observed or a machine error occurs.

All vital sign, body weight, and height measurements will be presented in a data listing. The actual values and change from baseline values at each time point will be summarized by treatment group for the safety population, both in tabular format and as boxplots.

9.4 Physical Examination

A full physical examination will be conducted at screening to assess enrollment eligibility. Only participants that are considered as healthy by the investigator will be enrolled.

Physical examination at screening will include, at a minimum, assessment of height and weight, body temperature, and resting vital signs (including percent oxygen saturation by pulse oximetry), in addition to assessments needed to determine eligibility. Assessments will include general appearance and specific organ systems (head, eyes, ears, nose, throat/mouth, neck (HEENT), respiratory, cardiovascular, gastrointestinal and neurological systems, psychiatric, skin and lymphatics).

A focused physical examination will be performed to check eligibility criteria again at Visit 1 (Day 1), and subsequently if indicated by participant's medical complaint and will include assessments of body systems involved in the complaint. Focused physical examinations will be symptom directed.

Full physical examinations will be performed at Screening, and focused physical examinations will be performed at the timepoints indicated in the schedule of assessments (see [Section 15](#)).

All physical examination results will be presented in a data listing.

9.5 Electrocardiograms

A 12-lead ECG will be performed at screening using a machine that automatically calculates heart rate and determines intervals for PR, QRS, QT and QTc. Triplicate (unmarked) 12-lead ECGs will be obtained and averaged.

All 12-lead ECGs will be obtained after the participant has rested in a supine position for at least 10 minutes. All Triplicate ECGs will be taken approximately one minute apart. Measurements that deviate substantially from previous readings will be repeated immediately.

Single 12-lead ECG will be performed at the timepoints indicated in the schedule of assessments (see [Section 15](#)).

Actual values and changes from baseline for numeric ECG data will be summarized by visit and treatment group for participants in the safety population, both in tabular format and as boxplots.

Shift from baseline to the worst interpretation of ECG results (normal, abnormal (CS), abnormal (NCS) over all visits will be summarized by treatment group using the frequency count and percentage of participants in each category.

All ECG data will be presented in a data listing.

9.6 Immunogenicity

Whole blood samples on VAMS and serum samples will be collected for detection of ADA against RSM01 in capillary blood and venous serum, as specified in the schedule of assessments ([Section 15](#)). Samples on Day 1 will be collected prior to RSM01 administration.

The detection of ADA to RSM01 will be performed using a validated immunoassay method with tiered testing of screening, confirmatory, and titration. Confirmed positive antibodies may be further characterized.

ADA results will be summarized at the time of the primary analyses, when all participants reach Day 151. The following analyses will be conducted separately for both VAMS (secondary objective) and serum (exploratory objective).

The overall analysis of immunogenicity will focus on the following key parameters:

- Immunogenicity incidence and characterization
- Association with pharmacokinetics
- Association with TEAEs

The immunogenicity population used in the analysis is described in [Section 4.4](#).

9.6.1 Terms and Definitions

The detection of ADA to RSM01 will be performed using a validated immunoassay method with tiered testing of screening, confirmatory, and titration, i.e.:

1. All samples will undergo a screening test.
2. If the screening test is positive for ADA, the sample will undergo a confirmatory test. A sample that has a negative or not reportable (NR) screening result will not undergo further testing.
3. If the confirmatory test is positive, the sample will be analyzed to determine the titer. A titer result can be a quantifiable number or not reportable (“titer not reportable” or “TNR”).

The following terms and definitions will be applied in the immunogenicity analyses.

ADA status of a sample

- Baseline ADA negative sample: Screening or confirmatory test of the last sample before administration of study treatment indicates ADA is not detected.
- Baseline ADA NR sample: Screening or confirmatory test of the last sample before administration of study treatment indicates ADA is not reportable.
- Baseline ADA missing: No baseline sample was available for testing.
- Baseline ADA positive sample: Screening and confirmatory tests of the last sample before administration of study treatment indicates ADA is detected. The numeric titer will be reported unless the titer result is NR, which would be reported as positive TNR.
- Post-baseline ADA negative sample: Screening or confirmatory test of sample taken after administration of study treatment indicates ADA is not detected.

- Post-baseline ADA NR sample: Screening or confirmatory test of sample taken after administration of study treatment indicates ADA is not reportable.
- Post-baseline ADA missing: No post-baseline sample was obtained.
- Post-baseline ADA positive sample: Screening and confirmatory tests of sample taken after administration of study treatment indicates ADA is detected. The numeric titer will be reported unless the titer result is NR, which would be reported as positive TNR.

ADA status of a participant

- Baseline ADA negative participant: A participant with baseline ADA negative sample. A participant with NR or no baseline ADA sample is assumed to be baseline ADA negative.
- Baseline ADA positive participant: A participant with a baseline ADA positive or positive TNR sample.
- Post-baseline ADA positive participant: A participant with at least one post-baseline ADA positive or positive TNR sample. An ADA positive participant will be further classified as follows:
 - Treatment-emergent positive: Participant had a post-baseline ADA positive or positive TNR sample in a participant with a baseline ADA negative sample OR participant had a post-baseline ADA positive sample that is \geq 8-fold increase above baseline titer in a participant with a baseline ADA positive sample. Note that the baseline sample and at least one post-baseline sample must have reportable titer to assess whether pre-existing immunogenicity was treatment-boosted.
 - Treatment-emergent nonevaluable.
 - Treatment-emergent negative.
- Post-baseline ADA negative participant: A participant with no post-baseline ADA positive or positive TNR sample.
- Any ADA detected: Subjects in Baseline ADA Positive AND/OR Treatment-emergent.
- No ADA Detected: Subjects who are Baseline ADA negative AND either Post-baseline ADA negative OR no valid post-baseline results (excluded from immunogenicity population).

